8.3 Exploratory analyses

In addition to the primary efficacy analysis and the analyses of secondary endpoints, some or all of the exploratory analyses listed in Table 10 (3-year endpoints) and Table 11 (5-year endpoints) may also be performed. All exploratory endpoints on the FAP will be analyzed as described in Section 8.1, however, for analyses in only colon/rectum/left-sided/right-sided colon subjects, the strata will only be defined by stage. For analyses with subgroups based on adjuvant treatment, an interaction-term between randomization arm and a time-varying treatment indicator will be used considering that adjuvant treatment for some subjects starts post-randomization. In result tables for exploratory analyses, 95 % Cl's, unadjusted for multiple testing will be presented, but not p-values.

For the analyses on the PP3 and PP5 populations, stabilized inverse probability of treatment weights (IPTW) will be used to estimate the effect on the randomized population. The stabilized IPTW for each subject in the PP3 and PP5 populations will be calculated as the ratio between the probability of receiving the treatment that was received (ASA or Placebo) estimated from a logistic regression model without covariates, and the probability of receiving the treatment that was received (ASA or Placebo) estimated in a logistic regression model including the covariates age, sex, country, BMI, tumor location (colon/rectum), type of neoadjuvant treatment, ASA score, time from surgery until randomization, calendar time of randomization, platelet count at baseline, CEA at baseline, MSI status, BRAF V600E status, KRAS status, and tumor differentiation. The use of inverse probability of censoring weights (IPCW), in addition to the IPTW's, for the PP analyses has been considered, but deemed unsuitable for the ALASCCA trial data for several reasons: 1) The time-point for which a subject is to be considered non-compliant is not well-defined, and therefore an IPCW approach would demand strong assumptions and/or looking into the future for certain subjects, 2) Compliance (described in Section 4.8.2) is defined as a weighted average of the visit-specific compliance measurements over the whole study period, and censoring at the first visit-specific non-compliance would result in the censoring of a substantial number of subjects with an overall compliance of >80%, and 3) There are no relevant time-dependent covariates measured during follow-up to be included for capturing treatment-confounder feedback. Given the above considerations, the limitations of the suggested PP analysis approach must be highlighted when presenting the trial results.

A secondary or exploratory analysis involving the Mutation B subgroup may be subjected to sensitivity analysis to assess the impact of observations that may not represent true driver (cancer-relevant) variants. This may include repeating the analysis using a subset containing only high-confidence driver variants.

Table 10. Specification of variables and populations for the exploratory analyses in the ALASCCA trial for 3-year endpoints. Mutation A: PIK3CA exon 9 and 20 hotspot small mutations,

Mutation B: other PIK3CA, PIK3R1 and PTEN non-silent small mutations and focal/homozygous deletion of PTEN.

Specification	Time variable(s)	Event indicator(s)	Population	Subgroup
TTR between randomized arms	ttr3y	rec_status_3y	PP3	Mutation A
TTR between randomized arms	ttr3y	rec_status_3y	PP3	Mutation B
TTR and DFS between randomized arms	ttr3y, dfs3y	rec_status_3y, dfs_status_3y	FAP	Mutation A + Mutation B
TTR and DFS between randomized arms	ttr3y, dfs3y	rec_status_3y, dfs_status_3y	FAP	Clonal high- confidence drivers: Mutation A + Mutation B
TTR between randomized arms	ttr3y	rec_status_3y	FAP	Active treatment Mutation A vs Placebo Mutation A + Mutation B
TTR starting 6 months from randomization	ttr3y	rec_status_3y	FAP	Mutation A
TTR starting 6 months from randomization	ttr3y	rec_status_3y	FAP	Mutation B
TTR and DFS between randomized arms	ttr3y, dfs3y	rec_status_3y, dfs_status_3y	FAP	Mutation A, colon cancer
TTR and DFS between randomized arms	ttr3y, dfs3y	rec_status_3y, dfs_status_3y	FAP	Mutation A, rectal cancer
TTR and DFS between randomized arms	ttr3y, dfs3y	rec_status_3y, dfs_status_3y	FAP	Mutation A, left- sided colon cancer
TTR and DFS between randomized arms	ttr3y, dfs3y	rec_status_3y, dfs_status_3y	FAP	Mutation A, right- sided colon cancer
TTR and DFS between randomized arms	ttr3y, dfs3y	rec_status_3y, dfs_status_3y	FAP	Mutation A, neoadjuvant and/or adjuvant treatment received

Specification	Time variable(s)	Event indicator(s)	Population	Subgroup
TTR and DFS between randomized arms	ttr3y, dfs3y	rec_status_3y, dfs_status_3y	FAP	Mutation A, neoadjuvant and/or adjuvant treatment not received
TTR and DFS between randomized arms	ttr3y, dfs3y	rec_status_3y, dfs_status_3y	FAP	Mutation A, rectal cancer, any neoadjuvant treatment received
TTR and DFS between randomized arms	ttr3y, dfs3y	rec_status_3y, dfs_status_3y	FAP	Mutation A, rectal cancer, no neoadjuvant treatment received
TTR and DFS between randomized arms	ttr3y, dfs3y	rec_status_3y, dfs_status_3y	FAP	Mutation A, MSI-H
TTR and DFS between randomized arms	ttr3y, dfs3y	rec_status_3y, dfs_status_3y	FAP	Mutation A, MSS/MSI-L
TTR and DFS between randomized arms	ttr3y, dfs3y	rec_status_3y, dfs_status_3y	FAP	Mutation B, colon cancer
TTR and DFS between randomized arms	ttr3y, dfs3y	rec_status_3y, dfs_status_3y	FAP	Mutation B, rectal cancer
TTR and DFS between randomized arms	ttr3y, dfs3y	rec_status_3y, dfs_status_3y	FAP	Mutation B, left- sided colon cancer
TTR and DFS between randomized arms	ttr3y, dfs3y	rec_status_3y, dfs_status_3y	FAP	Mutation B, right- sided colon cancer
TTR and DFS between randomized arms	ttr3y, dfs3y	rec_status_3y, dfs_status_3y	FAP	Mutation B, neoadjuvant and/or adjuvant treatment received
TTR and DFS between randomized arms	ttr3y, dfs3y	rec_status_3y, dfs_status_3y	FAP	Mutation B, neoadjuvant and/or adjuvant treatment not received
TTR and DFS between randomized arms	ttr3y, dfs3y	rec_status_3y, dfs_status_3y	FAP	Mutation B, rectal cancer, any neoadjuvant treatment received

Specification	Time variable(s)	Event indicator(s)	Population	Subgroup
TTR and DFS between randomized arms	ttr3y, dfs3y	rec_status_3y, dfs_status_3y	FAP	Mutation B, rectal cancer, no neoadjuvant treatment received
TTR and DFS between randomized arms	ttr3y, dfs3y	rec_status_3y, dfs_status_3y	FAP	Mutation B, MSI-H
TTR and DFS between randomized arms	ttr3y, dfs3y	rec_status_3y, dfs_status_3y	FAP	Mutation B, MSS/MSI-L
TTR and DFS between randomized arms	ttr3y, dfs3y	rec_status_3y, dfs_status_3y	FAP	Colon cancer
TTR and DFS between randomized arms	ttr3y, dfs3y	rec_status_3y, dfs_status_3y	FAP	Rectal cancer
TTR and DFS between randomized arms	ttr3y, dfs3y	rec_status_3y, dfs_status_3y	FAP	Left-sided colon cancer
TTR and DFS between randomized arms	ttr3y, dfs3y	rec_status_3y, dfs_status_3y	FAP	Right-sided colon cancer

Table 11. Specification of variables and populations for the exploratory endpoints in the ALASCCA trial for 5-year endpoints. Mutation A: PIK3CA exon 9 and 20 hotspot small mutations, Mutation B: other PIK3CA, PIK3R1 and PTEN non-silent small mutations and focal/homozygous deletion of PTEN.

Specification	Time variable	Event indicator	Population(s)	Subgroup
TTR between randomized arms	ttr5y	rec_status_5y	FAP and PP5	Mutation A
TTR between randomized arms	ttr5y	rec_status_5y	FAP and PP5	Mutation B
TTR and OS between randomized arms	ttr5y, os5y	rec_status_5y, os_status_5y	FAP and PP5	Mutation A + Mutation B
OS between randomized arms	os5y	os_status_5y	PP5	Mutation A

Specification	Time variable	Event indicator	Population(s)	Subgroup
OS between randomized arms	os5y	os_status_5y	PP5	Mutation B

9 Quality assurance of statistical programming

At the start of any code file there will be a comment specifying the author, date of file creation, date(s) and details of any file updates, reference to any parent code file that runs the child code file, references to input and output files.

A second statistician will review the code producing the data processing, and the primary and secondary efficacy analyses.

The statistical software R (R Foundation for Statistical Computing) will be used, in a version released less than a year before the time of analysis of the primary and secondary endpoints.

10 Listing of tables and figures

Note that the table and figure numbering in the below sections does not necessarily reflect the actual numbering in future publications. Some of the tables and figures may be published separately and in different order. Table formatting, e.g. number of decimals/significant digits, headings, row ordering etc. may be changed to follow the specifications of the selected journal(s).

Table 12. List of tables.

Table	Description	Population	Columns
Table 1.	Patient characteristics for randomized subjects in the ALASCCA trial.	FAP	Randomized to ASA Randomized to Placebo
Table 2.	Results from analysis of primary endpoint, and secondary endpoint 1-3. If the PHA is violated, one HR per time-interval (in addition to the overall HR).	FAP	N per randomized arm, no. of events per randomized arm, HR, 95% CI, p-value
Table 3.	Results from analysis of secondary endpoints 4-5.	FAP	N per randomized arm, no. of events per randomized arm, HR, 95% CI, p-value
Table 4.	Results from analyses of exploratory endpoints.	FAP/PP3	N per randomized arm, no. of events per randomized arm, HR, 95% CI
Table 5.	SAEs per randomized arm.	SP	Number of SAEs per randomized arm
Table 6.	AEs per randomized arm.	SP	Number of AEs per randomized arm
Supplementary Table 1.	Number of AEs per randomized arm and visit, stratified by type of AE.	SP	Number of AEs per randomized arm

Table 13. List of figures. Mutation A: Mutation in PIK3CA exons 9/20, Mutation B: Mutation in PIK3CA (other exons), PIK3R1, PTEN.

Figure	Description	Population	Axis labels (if applicable)
Figure 1.	CONSORT flowchart showing number of screened patients, exclusions, randomized subjects.		
Figure 2a.	CIF curves, with 95% CIs, comparing TTR assessed at 3 years between ASA and Placebo in subjects with somatic alterations in PIK3CA (exons 9/20).	FAP, Mutation A	X-axis "Months from randomization" Y-axis "Cumulative incidence of CRC recurrence (%)"
Figure 2b.	CIF curves, with 95% CIs, comparing TTR assessed at 3 years between ASA and Placebo in subjects with somatic alterations in PIK3CA (other exons), PIK3R1, or PTEN.	FAP, Mutation B	X-axis "Months from randomization" Y-axis "Cumulative incidence of CRC recurrence (%)"
Figure 3a.	KM curves, with 95% CIs and risk table, comparing DFS assessed at 3 years between ASA and Placebo in subjects with somatic alterations in PIK3CA (exons 9/20).	FAP, Mutation A	X-axis "Months from randomization" Y-axis "Net proportion of DFS (%)"
Figure 3b.	KM curves, with 95% CIs and risk table, comparing DFS assessed at 3 years between ASA and Placebo in subjects with somatic alterations in PIK3CA (other exons), PIK3R1, or PTEN.	FAP, Mutation B	X-axis "Months from randomization" Y-axis "Net proportion of DFS (%)"
Figure 4.	CIF curves, with 95% CIs, comparing TTR assessed at 3 years between ASA and Placebo.	FAP, Mutation A + Mutation B	X-axis "Months from randomization" Y-axis "Cumulative incidence of CRC recurrence (%)"
Figure 5a.	KM curves, with 95% CIs and risk table, comparing OS assessed at 5 years between ASA and Placebo in subjects with somatic alterations in PIK3CA (exons 9/20).	FAP, Mutation A	X-axis "Months from randomization" Y-axis "Net survival (%)"
Figure 5b.	KM curves, with 95% CIs and risk table, comparing OS assessed at 5 years between ASA and Placebo in subjects with somatic alterations in PIK3CA (other exons), PIK3R1, or PTEN.	FAP, Mutation B	X-axis "Months from randomization" Y-axis "Net survival (%)"
Figure 6.	KM curves, with 95% CIs and risk table, comparing OS assessed at 5 years between ASA and Placebo.	FAP, Mutation A + Mutation B	X-axis "Months from randomization" Y-axis "Net survival (%)"
Supplementary Figure 1.	KM curves, with 95% CIs and risk table, comparing TTR assessed at 3 years between ASA and Placebo in subjects with somatic alterations in PIK3CA (exon 9/20).	FAP, Mutation A	X-axis "Months from randomization" Y-axis "Net proportion of CRC recurrence (%)"

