4.5.2 Updated calculation in protocol version 5.2

An updated sample size calculation was included in the ALASCCA Clinical Study Protocol Version 5.2 after 3206 patients had been screened. The three-year cumulative incidence of recurrence in the placebo arm was estimated to 18 % based on the Stage/Risk factor-specific estimates in Osterman and Glimelius (2018)^[1], and a 10 % drop-out rate was assumed. A total of 150 subjects in each arm would have to be included to detect a risk ratio (RR) of 0.38 for comparison between the ASA and placebo arms with 80 % power and a two-sided alpha of 0.05. Assuming 15 % of screened patients have somatic alterations in the PIK3CA (exon 9 and/or 20) gene, a total of 3750 patients will have to be screened. The estimate of a 15 % mutation rate was based on the 3206 first screened patients. The sample size calculation was based on a two-sample test for proportions. Details of the initial sample size calculation are listed in Table 2.

Table 2. Details of the updated sample size calculation in protocol version 5.2.

Power (%)	80
Two-sided alpha (%)	5
Minimal follow-up (months)	36
Mutation rate (%)	15
3-year cumulative incidence of recurrence in the placebo arm (%)	18
RR	0.38
Number of subjects in each arm (incl. 10 % drop-out)	150
Number of subjects in each arm (excl. 10 % drop-out)	135
Number of patients needed to be screened	3750

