7.2 Safety interim analysis 2020

Data was extracted from the eCRF on January 17th, 2020, including subjects that were randomized up to and including October 21st, 2019, with follow-up up to and including January 17th, 2020. The safety report was sent to the SMC on March 5th, 2020.

The number of SAEs were summarized by randomized arm and visit. Fisher's exact test was used to test differences in frequencies of SAEs between randomized arms for each visit. Information on all SAEs were listed, see Table 8 for details. Similarly, the total number of AEs, and number of AEs per AE type (using the categories listed under "Type of SAE" in Table 8), were summarized by randomized arm and visit, and compared between arms for each visit using Fisher's exact test. The number of subjects with multiple AEs was also summarized by randomized arm, visit, and type of AE.

Table 8. SAE and AE details included in the 2018 and 2020 safety reports to the SMC

SAE variable	Categories
Visit number	4-9 (2018 report), 4-15 (2020 report)
SAE day	Day in relation to randomization date
Randomized arm	0/1 (not disclosing associated treatment)
Type of SAE	 Hematological
	 Cancer
	 Cardiovascular
	 CNS/Neurological
	 Dermatological
	- Endocrine
	 Eyes, ears, nose, throat
	 Gastrointestinal
	Urogenital
	Hormonal
	Immunological
	 Musculoskeletal
	Respiratory
	– Other
SAE description	 Leads to death
	 Is life threatening
	Other important medical event
	 Requires hospitalization for more than 24
	hours or extended medical care
	Causes permanent or significant
	invalidity/functional impairment
Intensity	– Mild
	- Moderate
T (185)	- Severe
Treatment modification	- Unchanged
	- Stopped
B "	Other, e.g., treatment pause
Result	- Restored
	- Under improvement
	Not Restored, with sequels
	Death

8 Analysis of trial endpoints

All tests and confidence intervals (CIs) will be two-sided. The significance level will be 5 %, and CIs will have 95 % confidence level. The endpoints and their respective variables and populations are summarized in Table 9.

Table 9. Specification of variables and populations for the primary endpoint or secondary endpoints 1-5 in the ALASCCA trial. Mutation A: PIK3CA exon 9 and 20 hotspot small mutations, Mutation B: other PIK3CA, PIK3R1 and PTEN non-silent small mutations and focal/homozygous deletion of PTEN.

Endpoint	Specification	Time variable	Event indicator	Population	Subgroup

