Adjuvant chemotherapy in colon	Fluorouracil/capecitabin						
cancer	Fluorouracil/capecitabin + oxaliplatin						
	Other adjuvant chemotherapy						
	No adjuvant chemotherapy						
	Missing						
Adjuvant chemotherapy in rectal	Fluorouracil/capecitabin						
cancer	Fluorouracil/capecitabin + oxaliplatin						
	Other adjuvant chemotherapy						
	No adjuvant chemotherapy						
	Missing						

¹V600E ²Exons 12, 13, 59, 61, 117 and/or 146

Table 15. Table template for Table 2: Results from analysis of primary endpoint, and secondary endpoint 1-3. If the PHA is violated, one HR per time-interval (in addition to the overall HR).

Outcome	N (n events) in ASA arm	N (n events) in Placebo arm	HR ASA vs Placebo (95% CI; p)
TTR in PIK3CA exons 9/20			
DFS in PIK3CA exons 9/20			
TTR in PIK3CA (other exons), PIK3R1, PTEN			
DFS in PIK3CA (other exons), PIK3R1, PTEN			

Table 16. Table template for Table 3: Results from analysis of secondary endpoints 4-5.

Outcome	N (n events) in ASA arm	N (n events) in Placebo arm	HR ASA vs Placebo (95% CI; p)
OS in PIK3CA exons 9/20			
OS in PIK3CA (other exons), PIK3R1, PTEN			

Table 17. Table template for Table 4: Results from analysis of exploratory endpoints.

Outcome	Subgroup	N (n events) in ASA arm	N (n events) in Placebo arm	HR ASA vs Placebo (95% CI)
TTR	PIK3CA exons 9/20 (PP3 population)			
TTR	PIK3CA (other exons), PIK3R1, PTEN (PP3 population)			

Table 18. Table template for Table 5: Number of SAEs per randomized arm.

		Randomiz	ed to ASA	Randomized	to Placebo
		Number of SAEs (%)	N subjects in SP	Number of SAEs (%)	N subjects in SP
Total					
Time from randomization (months)	Median (IQR, min- max)				
Type of SAE	Hematological				
• •	Cancer				
	Cardiovascular				
	CNS/Neurological				
	Dermatological				
İ	Endocrine				

		Randomize	Randomized to ASA		to Placebo
		Number of SAEs (%)	N subjects in SP	Number of SAEs (%)	N subjects in SP
	Eyes, ears, nose, throat				
	Gastrointestinal				
	Urogenital				
	Immunological				
	Musculoskeletal				
	Respiratory				
	Other				
SAE description	Leads to death				
	Is life threatening				
	Other important				
	medical event				
	Requires				
	hospitalization for more than 24 hours or				
	extended medical care				
	Causes permanent or significant invalidity/functional				
	impairment				
Intensity	Mild				
•	Moderate				
	Severe				
Treatment modification	Unchanged				
	Stopped				
	Other, e.g. treatment				
	pause				
Result	Restored				
	Under improvement				

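### The SAP gives separate HRs and p-values for mutation groups A and B but plans no estimate of whether the ASA effect differs between them, and its pooled A+B models leave out mutation type

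*SAP*

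**What the plan says.** SAP Table 9 assigns the primary endpoint and secondary endpoints 1 and 4 to the Mutation A subset of the FAP, and secondary endpoints 2, 3 and 5 to the Mutation B subset. Each is analysed with the Section 8.1 Cox model, in which arm is the only covariate and the five strata are combinations of location and stage. Section 8 opens with "All tests and confidence intervals (CIs) will be two-sided. The significance level will be 5" per cent. The templates in Tables 15 and 16 give an HR, CI and p-value for each group; the row "TTR in PIK3CA (other exons), PIK3R1, PTEN" stands below the A rows in the same table.

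SAP Section 8.3 extends this model to the subgroups: "All exploratory endpoints on the FAP will be analyzed as described in Section 8.1". It makes one exception: "For analyses with subgroups based on adjuvant treatment, an interaction-term between randomization arm and a time-varying treatment indicator will be used". These analyses are optional and are reported with unadjusted 95% CIs and no p-values. The only other planned interaction is arm by time interval, used if proportional hazards fails (Section 8.1).

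Tables 10 and 11 and Figures 4 and 6 also pool A and B. Mutation type is one of the three randomization stratification factors (SAP 4.6, Table 3), but it is not among the strata listed in Section 8.1.

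**The concern.** Mutation type is the trial's biomarker. Protocol Section 8 says that the role of *PIK3R1* and *PTEN* in response to ASA is unknown and only hypothesised to match that of *PIK3CA*. SAP 4.7 masks the mutation type because different hypotheses attach to each. Readers will therefore ask whether the effect differs between A and B, and the planned output contains no estimate that answers this.

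Two p-values in the same table invite an informal comparison. With limited power in each group, one significant and one non-significant result is a common pattern even when the true effect is the same. Reading that pattern as a biomarker difference could misdirect conclusions about which alterations predict benefit.

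The pooled analyses raise a smaller, related point. They combine A and B without estimating whether the effects agree, and without the stratification factor that separates them.

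**Working it through.** **1. The plan's own figure.** Inputs from SAP 4.5.2: "A total of 150 subjects in each arm would have to be included to detect a risk ratio (RR) of 0.38"; "The three-year cumulative incidence of recurrence in the placebo arm was estimated to 18" per cent; "a 10 % drop-out rate was assumed"; "The sample size calculation was based on a two-sample test for proportions". The ASA risk is 0.18 × 0.38 = 0.0684. The pooled-variance formula for two proportions (two-sided 0.05, 80% power, no continuity correction) gives 136 per arm, against the plan's 135 (150 × 0.9). Power at 135 per arm is 79.7%, so the plan's figure is reproduced. The equivalent exponential HR is ln(1 − 0.0684)/ln(1 − 0.18) = 0.357.

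**2. Assumptions for group B.** The documents give no placebo risk for B, so 18% is assumed. Protocol 10.1 gives B 150 per arm with 20% drop-out, which is 120 evaluable. The base case uses 135 in both groups; step 5 varies both inputs.

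**3. Power per group.** With placebo risk p1 = 0.18, p2 = 1 − 0.82^HR and expected events d = 135 × (p1 + p2), Schoenfeld power is P = Φ(√(d/4) × |ln HR| − 1.96). At HR 0.5, p2 = 0.0945, d = 37.1 and P = Φ(0.15) = 0.559.

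**4. Chance that exactly one group is significant, same true effect in both.** This is PA(1 − PB) + PB(1 − PA), or 2P(1 − P) with equal power, where P is the chance of a significant benefit.

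| Common effect | P, Schoenfeld | Exactly one, Schoenfeld | P, proportions | Exactly one, proportions |
|---|---|---|---|---|
| HR 0.357 (RR 0.38) | 0.847 | 26% | 0.797 | 32% |
| HR 0.5 | 0.559 | 49% | 0.533 | 50% |
| HR 0.6 | 0.361 | 46% | 0.350 | 46% |
| HR 0.7 | 0.210 | 33% | 0.206 | 33% |
| HR 0.8 | 0.111 | 20% | 0.111 | 20% |
| HR 1.0 | 0.025 | 5% | 0.025 | 5% |

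A simulation with Cox models (4,000 trials per effect) gave 31.9% at HR 0.357, 49.1% at HR 0.5, 32.7% at HR 0.7 and 4.0% at HR 1.0. With equal power, a significant result in A and not in B makes up half of each figure: 13–16% at RR 0.38 and about 25% at HR 0.5.

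**5. Sensitivity to group B (Schoenfeld).** With 120 per arm in B: 29% at HR 0.357 and 50% at HR 0.5. With 135 per arm and B's placebo risk moved from 10% to 25%: 43% down to 19% at HR 0.357, and 52% down to 48% at HR 0.5.

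**6. What a direct contrast would give.** In the same simulations an arm × mutation-group test rejected in 4.7–5.3% of trials with identical effects. Its precision is limited. At HR 0.5 in both groups the SE of the log ratio of HRs is √(4/37 + 4/37) = 0.465, and exp(1.96 × 0.465) = 2.49. For HR 0.5 in A against 1.0 in B (37.1 and 48.6 events), SE = √(4/37.1 + 4/48.6) = 0.436 and power = Φ(0.693/0.436 − 1.96), about 36%. For 0.357 against 1.0 it is about 63%.

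**7. Count in Table 10.** There are 10 subgroup rows in A and 10 in B, each with TTR and DFS, giving 40 HRs. The rows for neoadjuvant and/or adjuvant treatment received or not received account for 2 rows × 2 groups × 2 endpoints = 8, which fall under the planned interaction term. That leaves 32 without one, plus 8 pooled HRs by location and side (4 rows × 2).

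**The case against.** The strongest reply is that the plan never sets out to compare A with B. Every efficacy objective in SAP 4.2 is ASA versus placebo within one mutation group, and Protocol 10.1 says that B is analysed separately. A reader might infer that the SAP intends to claim a difference, or that Table 10 will be read through p-values. Neither is supported: no such claim is planned, and Section 8.3 withholds p-values from the exploratory results. For Table 10 the problem arises only if readers judge by whether a CI excludes 1.

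Nor is information lost for A versus B. The groups are disjoint, because SAP 4.9.6 places subjects with both alteration types in A. Anyone can form the ratio of HRs and its CI from Table 15. This stands, and it makes the gap one of reporting and interpretation rather than of data or validity.

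It is also true that an interaction test would be underpowered. But a wide CI for the ratio shows that uncertainty openly, whereas two p-values side by side conceal it.

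On the pooled strata, Section 8.1 refers in general terms to the covariates used in randomization, which might be read as taking in mutation type once the groups are combined. The strata it then lists do not include it, and Section 8.3 does not add it.

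**Conclusion.** The point holds in a limited form. No arm × mutation-group contrast is planned, most Table 10 pairs lack one, and the pooled models as written omit a randomization factor. With the same true effect in both groups, a split in significance would occur in about 26–32% of trials at the current design effect, about 50% near HR 0.5 and about 20% at HR 0.8, in either direction. This rests on 18% placebo risk and 135 per arm in both groups; the group B values are assumptions, with ranges in step 5.

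Two stronger readings should be resisted. A reader might infer that a split is to be expected in about half of trials. That is close to the ceiling and needs a common HR near 0.5 to 0.6; HR 0.5 was the superseded design effect (SAP 4.5.1). A reader might also infer that no subgroup interaction is planned at all, but Section 8.3 plans one for the adjuvant-treatment subgroups. The primary analysis is unaffected. No size is put on the omission of mutation type from the pooled strata, which is a matter of matching the analysis to the randomization.

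**What to change.** In SAP 8.3:

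1. Stratify pooled A+B Cox models by mutation group as well as location and stage. The Table 10 row setting ASA in A against placebo in A and B needs separate treatment, because B placebo subjects would have no ASA comparator within their strata.
2. Fit a pooled model with arm and arm × mutation group. Handle mutation group through the strata, with no main effect, since that would not be estimable. Report the A/B ratio of HRs with 95% CI for TTR, DFS and, when due, OS.
3. Do the same for Table 10 pairs defined by baseline factors (location, side, MSI, neoadjuvant treatment). Include a subgroup main effect only where the subgroup is not already a stratum.
4. State that no claim of a different effect rests on comparing separate HRs, CIs or p-values.

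The cost is a few lines of code and a table column; no new data are needed and the primary analysis does not change. The drawback is imprecision (step 6), so the SAP should also say that a null interaction is not evidence of equal effect. If this is added after unblinding, it must be labelled post hoc.
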